4.4 Subject Completion/Withdrawal

Subjects will be followed (Section 4.2) until:

- Five years after completing treatment
- Relapse

Protocol number: CHP12ST051
Amendment number:
Version date: April 2, 2013

- Death from any cause

Subjects may voluntarily withdraw from this study at any time but should complete the standard of care chemotherapy regimen and resection of their primary and metastatic tumor as described in this protocol.

5. STUDY ENDPOINTS AND EVALUATIONS

The timing of study endpoints, as well as standard of care procedures, is shown in the Schedule of Study Procedures.

5.1 Primary Endpoints

- Urinary biomarkers of acute kidney injury (KIM-1, NAG, NGAL) after each course of cisplatin (days 2 and 7) and each HDMTX infusion (24 h and day 7) on cycles 1-4 compared to baseline (pre-infusion) values
- Serum cystatin-C and creatinine prior to each course of cisplatin and each HDMTX infusion on cycles 1-4 and post-infusion cystatin-C and BMP if serum creatinine increases by $\geq 50\%$ compared to pre-infusion baseline value
- FEMg (simultaneous serum and spot urine for Mg and creatinine) prior to the start of the cisplatin infusions on days 1&2 and day 7 of cycles 1-4
- Plasma and urine MTX concentrations at the end of each HDMTX infusion on cycles 1-4
- Audiograms prior to cycles 1-4 and at the end of therapy.

5.2 Secondary Endpoints

- The incidence and severity (CTCAE v.4 grade) of safety events listed in Section 5.4,
- Response of the primary tumor to the first 2 treatment cycles will be assessed by quantifying the change in tumor volume on MRI after treatment relative to the pre-treatment tumor volume using the log ratio method [$\log(V_t/V_0)$, where V_t is tumor volume post-treatment and V_0 is tumor volume at baseline]¹⁰⁹ and quantifying the percent tumor necrosis in the resected tumor specimens histologically,
- The new biomarkers of AKI (KIM-1, NAG, NGAL) and GFR (cystatin C) will be correlated with the current standard clinical laboratory methods of assessing renal function with serum creatinine, estimated creatinine clearance, urinalysis and FEMg,
- A tissue microarray will be constructed from the paraffin blocks containing the initial biopsy specimen, the resected primary tumor and resected metastatic lesion (if available) in the Pathology Core Laboratory. A slide cut from the top of the block will be used to identify areas of viable tumor, which will then be marked on the block. IHC staining will be performed for proteins responsible for resistance to MAP agents and for protein targets of new agents under development,
- Serum bone specific alkaline phosphatase will be measured at baseline, pre- and post-op, end of treatment and at the time of relapse and correlated with tumor volume,

Protocol number: CHP12ST051
Amendment number:
Version date: April 2, 2013

- An osteosarcoma-specific patient reported outcome survey (Appendix 3) developed for this study will be administered prior to each treatment cycle, prior to surgery and at the end of therapy,
- Weight, arm circumference (muscle mass), skin fold thickness (body fat), pre-albumin, and use of supplemental feedings via NG tube or G-tube will be used to assess the impact of treatment on nutritional status over the course of therapy.

5.3 Efficacy Evaluations

- The effect of prolonging the duration of the HDMTX infusion to 12 h will be assessed by comparing urinary biomarkers of AKI and serum cystatin C and creatinine measured prior to, 24 h and 7 days after the start of each HDMTX infusion (n=8). All subjects will receive four HDMTX infusion durations of 4 h and four HDMTX infusion durations of 12 h in this crossover design, and subjects will serve as their controls. Measurement of the urine MTX concentration at the end of the infusion will be used to determine whether urinary MTX concentrations exceed the solubility limit for each HDMTX infusion.
- The effect of IV pantoprazole on cisplatin nephrotoxicity will be assessed by comparing urinary biomarkers of AKI, FEMg and serum cystatin C and creatinine measured prior to, at the end of the day 2 infusion, and on day 7 each cisplatin course (n=4). All subjects will receive cisplatin with and without pantoprazole in this crossover design, and subjects will, therefore, serve as their controls.
- The effect of IV pantoprazole on cisplatin ototoxicity will be assessed by comparing audiograms performed prior to each cisplatin infusion and at the end of therapy. All subjects will receive cisplatin with and without pantoprazole in this crossover design, and subjects will, therefore, serve as their own controls.
- Event-free and overall survival will be monitored but are not scientific objectives on this trial. An event is defined as tumor progression, relapse or death from any cause.

5.4 Safety Evaluations

- More than 90% of patients receiving MAP chemotherapy will experience severe (CTCAE grade 3 or 4) acute toxicity. The most common acute toxicities are nausea and vomiting, neutropenia, thrombocytopenia, fever/infection, oral mucositis, and hepatotoxicity (elevated serum transaminases and bilirubin).^{14,16,23} Neutropenic fever or infection necessitates hospital admission and empirical antibiotics.
- The following adverse events will be tracked by treatment cycle:
 - Nadir neutrophil count and duration of severe (ANC <500/mcL) neutropenia
 - Nadir platelet count and number of platelet transfusions
 - Hospital admissions/days for neutropenia with fever or infection
 - Highest value for serum ALT and total bilirubin
 - Grade 3 or 4 mucositis

Protocol number: CHP12ST051
Amendment number:
Version date: April 2, 2013

- Treatment delays or missed chemotherapy doses to allow for recovery from toxicity
- Dose modifications for toxicity
- Deaths attributed to chemotherapy toxicity
- After the first 12 patients have completed therapy, the incidence and severity of the events listed above as well as the nephrotoxicity and ototoxicity endpoints will be assessed by Cycle according to HDMTX infusion duration (4 h vs. 12 h) and according to whether or not IV pantoprazole was administered with cisplatin to ensure that the experimental dosing methods are not associated with excessive toxicity.
- After the first 12 patients have undergone resection of their primary tumor, the radiographic response (log ratio) and histologic response (% necrosis) will be assessed according to HDMTX infusion duration (4 h vs. 12 h) during Cycles 1 & 2 and according to whether or not IV pantoprazole was administered with cisplatin during Cycles 1 & 2 to ensure that the anti-tumor effect of the MAP chemotherapy regimen is not compromised by the experimental dosing methods.

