SAFETY EVALUATION	
Nadir neutrophil count and duration of severe (ANC <500/mcL) neutropenia, nadir platelet count and number of platelet transfusions, hospital admissions/days for neutropenia with fever or infection, highest value for serum ALT and total bilirubin, grade 3 or 4 mucositis, treatment delays or missed chemotherapy doses to allow for recovery from toxicity, dose modifications for toxicity, and deaths attributed to chemotherapy toxicity will be monitored and collected by cycle.
 
After the first 12 patients have completed therapy, the incidence and severity of the events listed above as well as the nephrotoxicity and ototoxicity endpoints will be assessed by Cycle according to HDMTX infusion duration (4 h vs. 12 h) and according to whether or not IV pantoprazole was administered with cisplatin to ensure that the experimental dosing methods are not associated with excessive toxicity.
 
After the first 12 patients have undergone resection of their primary tumor, the radiographic response (log ratio) and histologic response (% necrosis) will be assessed according to HDMTX infusion duration (4 h vs. 12 h) during Cycles 1 & 2 and according to whether or not IV pantoprazole was administered with cisplatin during Cycles 1 & 2 to ensure that the anti-tumor effect of the MAP chemotherapy regimen is not compromised by the experimental dosing methods.

Protocol number: CHP12ST051

Amendment number:

Version date: April 2,, 2013

STATISTICAL AND ANALYTIC PLAN	
This pilot study uses a 2 x 2 factorial, randomized crossover design, which will allow patients to serve as their own control. Nephrotoxicity data will be analyzed by course for cisplatin and by dose for HDMTX, and ototoxicity data will be analyzed by cycle.
 
The primary endpoints are sensitive urinary biomarkers of AKI, standard renal function tests, and audiograms, and all endpoints will be analyzed as continuous variables.
 
Twenty-four patients will be enrolled and patients serve as their own control. Over the past 5 years, 57 newly diagnosed patients with osteosarcoma were seen and treated at CHOP. This is an average of 11.5 patients per year, indicating that we can complete accrual to this study in about two years. For each primary endpoint, separate linear mixed effects models will be constructed for comparison of cisplatin with vs. without pantoprazole and for comparison of the 4 vs. 12 h infusion durations of HDMTX.

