3.1.5 Dose Modifications

Modification of the doses of cisplatin, doxorubicin, and HDMTX is required if toxicity for the drugs exceeds the thresholds listed in the Tables below on a prior treatment cycle. The percent of full protocol prescribed dose should be recorded on the TDM in the column labeled “% Dose”. If the dose is reduced by 25%, then the % Dose should be recorded as 75% (75% of the full dose).

Cisplatin:

Toxicity	Severity	Modification
Ototoxicity	>30 dB threshold at 2 kHz	Discontinue cisplatin
Nephrotoxicity	Serum creatinine >ULN for age and gender OR creatinine clearance <70 mL/min/1.73 m ²	Hold cisplatin until criterion in Section 3.1.4 is met
Neuropathy*	Grade >2 motor or sensory neuropathy	Hold cisplatin until resolved to grade ≤2

* See Appendix 2 for toxicity grading scale

Doxorubicin:

Toxicity	Severity	Modification
Myelosuppression	Planned day 22 HDMTX is delayed by >10d (cycle day >32) due to ANC <250/mcL or platelet count <50,000/mcL	Reduce doxorubicin dose by 20%
Cardiotoxicity	SF <27% (confirmed with repeat Echocardiogram 1 week later)	Hold doxorubicin until recovery to SF >28%
Mucositis	Grade 4 related to doxorubicin	Reduce doxorubicin dose by 20%

HDMTX:

Toxicity	Severity	Modification
Nephrotoxicity	Serum creatinine >ULN for age and gender OR creatinine clearance <70 mL/min/1.73 m ²	Hold HDMTX. Omit dose if renal function has not recovered after a 7-day delay
Mucositis	Grade 4 related to HDMTX	Reduce HDMTX by 50%

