6.1 Statistical Analysis Plan

6.1.1 Primary Endpoints

- **Urinary KIM-1, NAG and NGAL** will be normalized to the urinary creatinine concentration measured in the same urine specimen and expressed as ng/mg Cr. The end of infusion and 7-day post values for each biomarker will be analyzed by course for cisplatin with vs. without pantoprazole and by dose for HDMTX administered as a 4 h vs. 12 h infusion.
- **GFR** will be estimated from serum creatinine and from the cystatin C (see Section 1.3.3) prior to each course of cisplatin and each dose of HDMTX and 7-days post treatment. A decrease in the GFR will reflect toxicity from the immediately preceding course of

Protocol number: CHP12ST051
Amendment number:
Version date: April 2, 2013

cisplatin or dose of HDMTX. Change in GFR will be analyzed by course for cisplatin with vs. without pantoprazole and by dose for HDMTX administered as a 4 h vs. 12 h infusion.

- Change in **FEMg** from pre-dose 1 (day 1 of cycles 1-4) of cisplatin to pre-dose 2 (day 2 of cycles 1-4) of cisplatin and day 7 will be measured for each cycle containing cisplatin (n=4). Change in FEMg will be analyzed by course for cisplatin with vs. without pantoprazole to assess renal tubular toxicity.
- The **urinary MTX concentration** at the end of each HDMTX infusion on cycles 1-4 will be tabulated for the 4 and 12 h infusion durations and compared to the MTX solubility limit for the urine pH to determine whether the solubility limit was exceeded. End infusion urine MTX concentration will also be correlated with simultaneous serum concentration and with the severity of renal toxicity as measured by AKI biomarkers and serum creatinine and serum cystatin C.
- An **audiogram** will be performed prior to Cycles 1, 2, 3 and 4 and at the end of therapy (after cycle 6). The average hearing level (HL) threshold in dB over the frequency range of 4,000-8,000 Hz will be derived separately for each ear from each audiogram. The increase in the average HL threshold in dB from the pre-cycle 1 to pre-cycle 2, from pre-cycle 2 to pre-cycle 3, from pre-cycle 3 to pre-cycle 4, and from pre-cycle 4 to end of therapy audiograms will be derived and this increase in HL threshold will be compared for cisplatin with vs. without pantoprazole.

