6.1.2 Secondary Endpoints

- **Common grade ≥ 2 toxicities** from cisplatin + doxorubicin (other than cisplatin nephrotoxicity and ototoxicity), including myelosuppression, mucositis, nausea and vomiting leading to dehydration requiring IV fluid hydration, peripheral neuropathy, cardiac dysfunction, and treatment delays due to toxicity will be collected and graded according to CTCAE v.4. Similarly, HDMTX-related grade ≥ 2 toxicities (other than nephrotoxicity), including myelosuppression, mucositis, dermatitis, hepatotoxicity and neurotoxicity will be collected and graded. The incidence and severity (grade) of toxicities will be tabulated and compared by treatment arm (with vs. without

pantoprazole for cisplatin + doxorubicin and by infusion duration for HDMTX).

- **Response** to 2 cycles of neoadjuvant chemotherapy will be assessed radiographically and histologically.
 - The volume of the tumor on MRI will be measured pretreatment and pre-operatively (post-cycle 2). The log ratio (Section 5.2) of the two measurements will be derived and compared using a non-parametric analysis for cisplatin with (patients on treatment arms 1 and 3) vs. without (patients on treatment arms 2 and 4) pantoprazole and for HDMTX administered as a 4 h infusion (treatment arms 1 and 2) vs. a 12 h infusion (treatment arms 3 and 4).
 - The tumor specimen that is removed after 2 cycles of neoadjuvant chemotherapy will be evaluated histologically and the percent of the tumor that is necrotic will be estimated from review of multiple sections. The percent necrosis will be compared using a non-parametric analysis for cisplatin with (patients on treatment arms 1 and 3) vs. without (patients on treatment arms 2 and 4) pantoprazole and for HDMTX administered as a 4 h infusion (treatment arms 1 and 2) vs. a 12 h infusion (treatment arms 3 and 4).
- **GFR** estimated from serum creatinine using the modified Schwartz formula will be correlated with GFR estimated from serum cystatin C (Section 1.3.3, the equation also includes serum creatinine and BUN). The presence and amount (normalized to creatinine concentration) of biomarkers of AKI in urine will be correlated with proteinuria, serum creatinine, and change in FEMg.

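### Section 5.4 counts dose modifications and delays by cycle although a prior cycle can trigger them, so at the crossover some are charged to the opposite treatment and the contrast on these two items is diluted

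*Combined protocol and SAP*

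**What the plan says.** Section 5.4 opens its list of safety items with "The following adverse events will be tracked by treatment cycle". The list has eight entries, among them "Treatment delays or missed chemotherapy doses to allow for recovery from toxicity" and "Dose modifications for toxicity". The synopsis repeats the by-cycle collection ("deaths attributed to chemotherapy toxicity will be monitored and collected by cycle"). After 12 patients have completed therapy, Section 5.4 says the listed events "will be assessed by Cycle according to HDMTX infusion duration (4 h vs. 12 h) and according to whether or not IV pantoprazole" was given with cisplatin.

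Section 3.1.5 says that modification of cisplatin, doxorubicin and HDMTX doses "is required if toxicity for the drugs exceeds the thresholds listed in the Tables below on a prior treatment cycle". It records the percentage of full dose on the treatment delivery map, whose layout (Appendix 1) has one line per administration.

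Section 3.1.4 sets start criteria for each cisplatin/doxorubicin course and for HDMTX. Sections 3.1.3 and 3.2 switch both randomised factors between cycles 2 and 3. Cycles 5 and 6 have no cisplatin, and their HDMTX duration depends on tolerance, so they lie outside the randomised comparison.

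For GFR, Section 6.1.1 does look back: "A decrease in the GFR will reflect toxicity from the immediately preceding course of" cisplatin or dose of HDMTX. Nothing equivalent is written for delays or modifications. Section 6.1.2 lists delays among the toxicities to be compared ("cardiac dysfunction, and treatment delays due to toxicity will be collected and graded according to CTCAE v.4") without saying which cycle a delay belongs to.

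**The concern.** A dose modification is a lagged event: the toxicity occurs in one cycle and the changed dose is given in a later one. If the event takes the treatment label of the cycle in which it is seen, the label is wrong whenever the treatment has changed in between. In this design that happens once per patient, at the move from cycle 2 to cycle 3.

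The protocol's own rules supply an example. In arms 3 and 4 HDMTX runs over 12 h in cycles 1 and 2 (Section 6.1.2). Under Section 3.1.5, grade 4 mucositis related to a cycle 2 infusion leads to a reduced HDMTX dose. That dose is first given in cycle 3, a 4 h cycle, so a by-cycle table shows a modification under 4 h that the 12 h infusion caused.

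The 12-patient review in Section 5.4 uses these counts. At the same point Section 6.3 lets the investigators discontinue an intervention on clinical judgement, without a statistical stopping rule. A judgement made from a small table depends on the table's labels being right.

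**Working it through.** The documents give no expected rate of delays or modifications, so there is no figure of the plan's to reproduce. All rates below are assumptions.

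**Set-up.** For either factor, half the patients follow AABB and half BBAA over cycles 1-4 (Section 3.2 balances the arms, 3 per arm in the first 12). Let a and b be the per-cycle risks of a triggering toxicity on A and B. An event triggered in cycle k is seen in cycle k+1.

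**Where each trigger lands**

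| Triggered in | Seen in | Label under the literal reading |
|---|---|---|
| 1 | 2 | correct |
| 2 | 3 | opposite treatment |
| 3 | 4 | correct |
| 4 | 5 | outside the comparison |

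**Each modification counted once, where seen (one patient per sequence)**
- By trigger: A = 4a, B = 4b.
- As labelled: A = 2a + b, B = 2b + a.
- Difference: a − b instead of 4(a − b), which is 25% of the true contrast with the same sign.
- At 20% and 10%: A = 0.40 + 0.10 = 0.50 and B = 0.20 + 0.20 = 0.40. The ratio is 1.25; the true ratio is 0.80/0.40 = 2.0.
- At 15% and 5%: 0.35 against 0.25. The ratio is 1.40 instead of 3.0.

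**Each reduced cycle counted, with reductions staying in force (20% and 10%)**
- AABB: cycle 2 = 0.20 (label A); cycle 3 = 1 − 0.8² = 0.36 (B); cycle 4 = 1 − 0.8² × 0.9 = 0.424 (B).
- BBAA: cycle 2 = 0.10 (B); cycle 3 = 1 − 0.9² = 0.19 (A); cycle 4 = 1 − 0.9² × 0.8 = 0.352 (A).
- A = 0.20 + 0.19 + 0.352 = 0.742. B = 0.36 + 0.424 + 0.10 = 0.884. The ratio is 0.84, so the sign reverses.

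**Risks that vary by cycle.** Let m1 to m4 multiply both risks in cycles 1-4.
- Counted once, the labelled difference is (a − b)(m1 − m2 + m3) and the true one is (a − b)(m1 + m2 + m3 + m4).
- Rising risks (0.5, 1, 1.5, 2) give 1/5 = 20% of the true contrast. Late risks (0, 0.2, 1, 1) give 0.8/2.2 = 36%.
- The sign changes only if m2 exceeds m1 + m3. For example, (1, 2.5, 1, 1) gives −0.5/5.5 = −9%.
- If every event is recounted in each later cycle, the labelled difference is (a − b)(−m1 − 2m2 + m3). Flat risks give −50%, and the late pattern gives 0.6/2.2 = +27%.

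**Twelve patients, 6 per sequence (50,000 simulated trials, flat 20% and 10%).** The observed difference has the wrong sign in about 30% of trials when each event is counted once where seen. With recounting it is about 55%. Attribution to the triggering cycle gives about 12% and 14% under the same two event models. Over assumed risks from 10%/5% to 40%/20% the ranges are 23-30%, 49-66% and 2-18%.

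**Delays.** Cycles 1-4 contain 12 dosing occasions (day 1, day 22 and day 29 in each of four cycles). A day 22 delay follows cisplatin/doxorubicin of the same cycle, and a day 29 delay can follow day 22 HDMTX of the same cycle. A delay crosses the switch mainly at one occasion, cycle 3 day 1. The figures above therefore describe modifications and do not apply to delays in general.

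**The case against.** The plan never says that events are counted where they appear. It says they are tracked and assessed by cycle and leaves attribution open. Section 6.1.2 is worded causally, separating cisplatin/doxorubicin toxicities from HDMTX-related ones, and Section 8.3 collects onset and attribution for related events of grade 2 or higher. This stands in part: the lag is the literal reading and not an explicit instruction. But neither section assigns a delay or modification to its triggering cycle.

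A reader might infer that the safety comparison as a whole can reverse. The documents do not support that.
- Six of the eight items (nadir neutrophils, nadir platelets, admissions, ALT and bilirubin, mucositis, deaths) do not depend on this lag, and several measure the triggering toxicities directly.
- Counting each modification once keeps the sign under flat risks. Reversal needs recounting, which the text does not prescribe, or a marked cycle 2 peak, for which it gives no evidence.
- Several Section 3.1.5 actions are holds until recovery and do not persist by rule. However, no re-escalation is described for the doxorubicin and HDMTX reductions, so recounting is not excluded either.
- Hearing loss at 4-8 kHz is described in Section 1.3.4 as starting above 300 mg/m² cumulative cisplatin. At 120 mg/m² per cycle that falls in cycle 3. Late triggers of this kind keep the sign even with recounting (+27% above).

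A reader might also infer that cardiac findings are mis-tallied, because routine echocardiograms fall before cycles 3 and 5. That does not hold. Cardiac dysfunction is not on the Section 5.4 by-cycle list, no text assigns a pre-cycle 3 echocardiogram to cycle 3 treatment, and footnote 5 of the Schedule of Study Procedures repeats the test before each doxorubicin course when the shortening fraction was below 30% on the prior cycle.

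Lastly, Section 6.3 names toxicity incidence and grade, plus response, and not dose modifications. These two items reach the 12-patient review through Section 5.4 and inform a judgement; they do not decide it alone.

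**Conclusion.** The point holds for two of the eight items tracked in Section 5.4. Followed literally, the by-cycle rule charges a modification, or a day-1 delay for toxicity, triggered in cycle 2 to the opposite treatment, and loses one triggered in cycle 4. The expected effect is dilution: with flat risks and each modification counted once, a quarter of the true difference remains (ratio 1.25 instead of 2.0 at 20% and 10%). Reversal (0.74 against 0.88) depends on recounting carried-forward reductions and should be described as possible under one permitted reading, not as expected.

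These sizes rest on assumed rates, independent triggers and balanced sequences. The text itself establishes the by-cycle tally, the prior-cycle trigger, the switch after cycle 2 and the lack of an attribution rule. The change should be made because it is cheap and the 12-patient review relies on judgement. It does not touch the primary endpoints.

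**What to change.** In Sections 5.4, 6.1.2 and 6.3, state that:
- each delay, missed dose and dose modification is attributed to the cycle and drug whose toxicity triggered it;
- each modification is counted once, at its trigger, however long it stays in force;
- events seen at cycle 5 but triggered in cycle 4 are included under the cycle 4 treatment;
- surgical or wound-healing delays before cycle 3 are recorded separately from delays for toxicity.

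The cost is one field for triggering cycle and drug on the treatment delivery map and eCRF, a reason code for the cycle 3 start, and a sentence in each of the three sections. No patients, visits or samples are added, and no dosing rule changes.
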